9.2.3. Serious Adverse Event Definition/Qualification

A SAE is defined as an AE that results in any of the following outcomes:

- Death (note that death is the outcome of a SAE and the cause of death should be listed as the AE)
- Life-threatening event
- In-patient hospitalization or prolongation of existing hospitalization
- A persistent or significant disability/incapacity
- Congenital anomaly or birth defect
- Any other important medical event that may not result in death, be life-threatening, or require hospitalization, may be considered a SAE when, based upon appropriate medical judgment, the event may jeopardize the pmlicipant and may require medical or surgical intervention to prevent one of the outcomes listed above. Examples of such medical events include allergic bronchospasm requiring intensive treatment in an emergency room or at home, blood dyscrasias or convulsions that do not result in in-patient hospitalization, or the development of drug dependency or drug abuse.

In the event of a SAE, the participant may be dropped from the study if the Clinical Investigator deems it necessary.

9.2.4. Serious Adverse Event Reporting Instructions

If in the opinion of the Clinical Investigator the event meets the criteria of a SAE the following procedures will be followed:

• The Clinical Investigator will report the SAE by telephone to Biofortis Innovation Services immediately upon becoming aware of the event.

- In addition, the initial SAE report should be submitted with other applicable information (such as medical history, concomitant medications, AEs) to Biofortis Innovation Services within 24 h of reporting the event to the attention of the Project Manager.
- The Clinical Investigator will also notify the Institutional Review Board (IRB) of the event within the parameters and timeframe specified under the IRB Standard Operating Procedures (SOP) after becoming aware of the SAE. An initial report followed promptly by a complete report will be forwarded to the IRB.
- Follow-up information relating to a SAE must be submitted to Biofortis Innovation Services by telephone, fax, or overnight courier as soon as additional data related to the event are available.
- If a subject is hospitalized or hospitalization is prolonged due to the SAE, the hospital discharge summary will be obtained if possible when it becomes available.
- If a death occurs and an autopsy is performed, a copy of the autopsy report will be obtained if possible when it becomes available. All efforts must be undertaken to obtain follow-up information promptly.
- Biofortis Innovation Services will report SAEs to the Sponsor per the terms of the Master Service Agreement.

9.2.5. Electronic CRF Recording of Adverse Events

All AEs will be recorded on the AE eCRF page. For participants who have an ongoing AE at their final study visit, a follow-up AE eCRF page will be collected after 30 d. Participants will be instructed to notify Biofortis Innovation Services immediately should new AEs emerge for an additional 30 d following their last day on the study diet. All SAEs must be recorded on the AE and SAE eCRF page.

9.2.6. Serious Adverse Event Follow-Up

For all SAEs occurring during the study or within 30 d of the study diet, the Clinical Investigator must submit follow-up reports to Biofortis Innovation Services regarding the participant's subsequent course. All SAEs that are ongoing at the end of the study or upon discontinuation of the participant's participation must be followed until either:

- The event resolves, or
- The event/condition has stabilized (e.g., in the case of persistent impairment), or
- The event returns to baseline, if a baseline value is available, or
- The participant dies, or
- The event can be attributed to other than the study treatment, or to other than the study conduct.

9.2.7. Pregnancy

The study foods being dispensed for consumption in this study are commercially available ingredients, safe for consumption by pregnant or lactating women. However, the outcome variables measured would be expected to be affected by pregnancy and lactation, and the caloric levels of the study meal plans are not appropriate for pregnant women. Additionally, the DXA scan involves a very small dose of radiation, which makes the test unsuitable for women who arc, or might be, pregnant. All female participants <60 years of age will undergo in-clinic urine pregnancy testing prior to every DXA scan. Pregnant or lactating women will be excluded from

Jason Pharmaceuticals, Inc. BI0-1607 (MED 019) 21 June 2016; Version 1.7 Confidential

122

the study and women of childbearing potential will be required to use appropriate contraceptive methods to avoid pregnancy. Documentation of contraception method must be recorded in the source chart.

Although pregnancy is not a SAE, all pregnancies occurring in mndomized participants will be reported within 24 h of notification. The Clinical Investigator will immediately notify the Principal Scientific Investigator and the IRB about the pregnancy. Should a female participant become pregnant at any time after randomization, the participant should be withdrawn from the study, and the Clinical Investigator will be required to follow the participant through the pregnancy term and report to Biofortis Innovation Services the course of the pregnancy including perinatal and neonatal outcomes.

10. Conduct of the Study

10.1. Ethics and Regulatory Considerations

This study will be conducted according to Good Clinical Practice Guidelines, the Declaration of Helsinki (2000), and US 21 CFR. Signed written informed consent for participation in the study will be obtained from all participants before protocol-specific procedures are carried out. Participants will be informed of their right to withdraw from the study at any time.

10.2. Institutional Review Board

The Clinical Investigator will ensure that an appropriately constituted IRB, in compliance with the requirements of 21 CFR 56, reviews and approves the clinical study. Before the study is started, the Clinical Investigator will forward copies of the protocol and consent form for this study to the IRB for review and approval. IRB approval must refer to the study by exact protocol title and number, identify the documents reviewed, and state the date of review. The IRB must be informed of all subsequent protocol amendments. No alterations, modifications to IRB-approved documents, including the protocol, protocol summary, consent form, recruitment materials and questionnaires will be allowed. The IRB must also be informed of all SAEs and of unexpected AEs that meet the IRB's reporting guidelines as outlined in the IRB's SOPs. In addition, the Clinical Investigator will immediately forward copies of all correspondence with the IRB to Biofortis Innovation Services.

10.3. Informed Consent and Protected Health Information

The study will be explained verbally as well as on the informed consent document. Each participant will be given ample opportunity to inquire about details of the study and to read and understand the consent form before signing it.

Consent must be documented by the dated signature of the participant. Each participant's signed informed consent document must be kept on file by the Clinical Investigator for possible inspection by regulatory authorities or by the Sponsor. The participant should receive a copy of the written informed consent document once he/she bas signed it.

The Sponsor recognizes the importance of protecting the privacy of participant data. Therefore, for study sites within the United States, the informed consent form will incorporate, or be accompanied by, a separate document incorporating HIPAA-compliant wording, by which

participants authorize the usc and disclosure of their Protected Health Information by the Clinical Investigator and by those persons who need that information for the purposes of this study.

A participant may not be admitted to the study unless informed consent of the participant (or her legally authorized representative) has been obtained.

10.4. Participant Confidentiality

The Clinical Investigator is responsible for ensuring that participants' anonymity will be maintained. Electronic CRFs or other documents will identify participants by initials, number, or code, and not by name. The Clinical Investigator will keep a separate log showing codes, names, and addresses. All documents showing the participants' identity will be kept in strict confidence by the Clinical Investigator. However, the Clinical Investigator agrees that the Sponsor, its employees or agents, the IRB, as well as representatives of the FDA, will have the right to audit and review pertinent medical records relating to this clinical trial and that the participants will provide written informed consent to this effect. Sponsor will also receive name and contact information for participants for the purpose of fulfilling study food orders (which are sent directly to the homes of participants) and for interactions with the Medifast Nutrition Support Team. Sponsor will ensure that participant information will be kept confidential and will not be used for any commercial purposes.

10.5. Withdrawal of Participants from the Study

Participants may be removed from the study for any of the following reasons:

- A participant requests discontinuation;
- The Clinical Investigator initiates removal for medical or compliance reasons;
- Occurrence of any AE or condition that could, in the Clinical Investigator's opinion, interfere with the evaluation of the treatment effect of the study food or put the participant at undue risk.

It is understood by all concerned that an excessive rate of withdrawals can render the study uninterpretable, therefore, unnecessary withdrawal of participants should be avoided. Should a participant decide to withdraw, all efforts will be made to complete and report observations as thoroughly as possible. In the event that a participant is withdrawn from the study, the reason for the withdrawal will be documented in the eCRF. Prior to a participant's withdrawal from the study, an attempt will be made to conduct an early termination visit, which will occur at week 16 and include the clinic visit procedures for Visit 7.

Note that any participant who achieves a BMI of $\leq 19 \text{ kg/m}^2$ will be placed on a weight maintenance diet and should not be withdrawn from the study.

II. Administrative Matters

All references to the Sponsor in this section include all designees e.g., Contract Research Organizations or Consultants acting on behalf of the Sponsor.

Jason Pharmaceuticals, Inc. BI0-1607 (MED 019) 21 June 2016; Version 1.7 Confidential

CANADA CONTRACTOR CONTRACTOR CONTRACTOR CONTRACTOR

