The interventions in this study are designed to mimic the TSFL and MEDD user experiences and will utilize the meal plans, Medifast products, and support options available for each of these programs. The TSFL and MEDD groups will be compared to a control group following a self-directed, food-based, reduced-calorie diet consistent with the 2015 Dietary Guidelines for Americans and based on the United States Department of Agriculture (USDA) ChooseMyPlate program.

4. Objectives

The primary objective of this study is to evaluate the effects of two commercially available weight loss programs, the TSFL and the MEDD programs, each compared to a self-directed control diet, on changes in body weight over a 16-week weight loss phase, in apparently healthy overweight and obese men and women.

Secondary objectives include, examining effects of each weight loss program compared to the seli directed control diet on changes in body composition, body circumference parameters, QoL, and biomarkers of inflammation over a 16-week weight loss phase. Relationships between changes in body weight with self-reported adherence and QoL assessments will also be examined. Additionally, participant perspectives on program satisfaction and sense of health/well-being will be assessed at the end of the study.

5. Study Sample

Participants will be apparently healthy men and women, 18-65 years of age, inclusive, each with a body mass index (BMI) of 27.0 to 42.0 kg/m², inclusive. No more than 10% of participants will be enrolled with a BMI 27.0 kg/m² and <30.0 kg/nl and no more than 25% of participants will be males.

6. Study Design and Procedures

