6.7. Early Termination Procedures

The term "Early Termination" refers to a participant's non-completion of the study. Should a participant decide to withdraw, all efforts will be made to complete and report observations as thoroughly as possible. In the event that a participant is withdrawn from the study, the reason for the withdrawal and the party who initiated the withdrawal (participant or Clinical Investigator) will be documented. Should the participant decide to withdraw, documentation of the early termination will be made and an attempt to conduct an early termination visit (which will occur at week 16 and include the clinic visit procedures for Visit 7).

The primary reason for a participant withdrawing prematurely should be selected fiom the following standard categories:

Adverse Event- event which results in discontinuation of the study food by the participant or that in the judgment of the Clinical Investigator for the best interest of the participant requires discontinuation of study food (includes all categories of study food relatedness; Not Related, Unlikely, Possibly, Probably, and Definitely).

Death -death of the participant.

Withdrawal of Consent- participant desires to withdraw from further participation in the study in the absence of a medical need to withdraw determined by the Clinical Investigator.

Lost to Follow-Up- participant did not return for one or more follow-up visit(s) following dispensing of test product and could not be contacted thereafter. The reason for withdrawal was unknown and could not be documented.

Other- causes of premature termination from the study other than the above, such as theft or loss of study foods, pregnancy, termination of study by Sponsor, etc.

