8.2. Statistical Analysis

8.2.1. Analysis Populations

An intent-to-treat (ITT) population will include all participants who were randomized into the study. A complete case population (i.e., completers) will include the subset of participants that completed the study on their assigned intervention. A modified ITT population will include all randomized participants that had a least one post-baseline weight measurement.

All decisions regarding exclusion from the outcome populations will be documented prior to database lock.

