## 8.0. OUTCOME ANALYSIS

### 8.1. Primary Outcome Variable

The primary outcome variable will be change (absolute and percent change) in body weight from baseline (Visit 2; week 0) to end of study (Visit 7; week 16)

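### Protocol 10.5 allows removal from the study for undefined compliance reasons, which risks informative and arm-dependent missing week-16 weights; the week-16 early termination visit only partly covers this.

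*Protocol*

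**What the plan says.** Protocol 10.5 gives three grounds for removing a participant from the study. The second reads "The Clinical Investigator initiates removal for medical or compliance reasons". It means leaving the study, not only stopping the diet, and it comes with no definition, threshold or rule for applying it equally across arms. The same section adds that "unnecessary withdrawal of participants should be avoided".

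On follow-up after withdrawal, 10.5 says that "an attempt will be made to conduct an early termination visit, which will occur at week 16", with the Visit 7 procedures, which include gown weight. It places this attempt before the withdrawal and also at week 16. Protocol 6.7 describes the same visit more narrowly: "Should the participant decide to withdraw, documentation of the early termination will be made and an attempt to conduct an early termination visit". For any withdrawal, 6.7 requires that "the party who initiated the withdrawal (participant or Clinical Investigator) will be documented". Its standard reasons are adverse event, death, withdrawal of consent, lost to follow-up and other. There is no compliance category there or in SAP Table 1.

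On analysis, Protocol 8.2.1 states: "An intent-to-treat (ITT) population will include all participants who were randomized into the study". SAP 5.0 limits Completers to those who completed every clinic visit. SAP 10.0 uses multiple imputation for the ITT population if data are at least missing at random (MAR), runs the mITT analysis with and without last observation carried forward, and imputes body weight only. By SAP 16.0, body composition, circumferences, hs-CRP and quality of life are tabulated for mITT without imputation and for Completers.

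Participants who reach a low BMI are treated differently. Under Protocol 6.8 and 10.5 they stop the weight loss diet but stay in the study and keep attending visits.

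**The concern.** Adherence follows from the assigned program and plausibly affects weight loss. Protocol section 4 plans to study that link: "Relationships between changes in body weight with self-reported adherence and QoL assessments will also be examined". Removing people on this ground can take out, on average, those who would have lost less weight. If it happens more in one arm, that arm's observed mean improves for reasons unrelated to the program.

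The opportunity to see non-adherence differs by arm. The TSFL schedule in Protocol 6.4.1 has a baseline session, 4 contacts in week 1, 2 in each of weeks 2 to 4, and one a week in weeks 5 to 16: 1 + 4 + 6 + 12 = 23. MEDD has one scheduled call. Control has no contact between visits. All arms complete the adherence scale at Visits 4 to 7, so non-adherence is visible everywhere, but less often outside TSFL.

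Most exposed are the Completers analyses, the mITT analysis without imputation, and the secondary outcomes that are never imputed. A reader of the final report could not easily judge the extent, because compliance removals would probably be counted under the category for other reasons.

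**Working it through.** **The plan's own figure.** Inputs from Protocol 8.1 and SAP 3.0: SD 15.0 lb, difference 9.0 lb, two-sided alpha 0.025 per comparison, power 80%.

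- Normal approximation: n = 2(2.241 + 0.842)² × 15² / 9² = 52.8, so 53 per group.
- t-based: 54.1, so 55 per group, with power 0.807 at 55. The stated 55 reproduces.
- 66 randomized per group implies an attrition allowance of 1 − 55/66 = 16.7%, with no split by cause. The sample size is not in dispute.

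**Illustrative shift.** Assumptions, none given by the documents: the least adherent share f of one active arm is removed, no one removed is weighed at week 16, adherence and weight loss are jointly normal with correlation r, and only observed weights are analyzed. Then

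shift = 15 × r × φ(z_f) / (1 − f), where z_f is the f-quantile of the standard normal.

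For 7 of 66 removed: f = 0.106, z_f = −1.248, φ = 0.183, so φ/(1 − f) = 0.205 and the shift is 3.07 × r lb.

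| Removed from one arm | r = 0.3 | r = 0.5 | r = 0.7 |
|---|---|---|---|
| 3 of 66 | 0.45 lb | 0.75 lb | 1.05 lb |
| 7 of 66 | 0.92 lb | 1.54 lb | 2.15 lb |
| 11 of 66 (whole allowance) | 1.35 lb | 2.25 lb | 3.15 lb |

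Simulating 7 of 66 gives 0.91, 1.50 and 2.1 lb, which is 10%, 17% and 23% of the 9 lb design difference.

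**Type I error with no true difference, 7 of 66 removed from one arm.** SE = 15 × √(1/66 + 1/59) = 2.69 lb. At r = 0.5 the shift is 1.54/2.69 = 0.57 SE. The rejection probability is 1 − Φ(2.241 − 0.572) + Φ(−2.241 − 0.572) = 0.0475 + 0.0025 = 0.050. Simulated t-tests give about 0.033, 0.05 and 0.08 at r = 0.3, 0.5 and 0.7, against a nominal 0.025. With 3 of 66 removed they give about 0.03 to 0.04.

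**What shrinks it.**

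- *Retrieval.* If half of those removed are weighed at week 16, the observed mean is [(1 − f) × m_keep + (f/2) × m_rem] / (1 − f/2). For 7 of 66 and r = 0.5, m_keep = 1.54 and m_rem = −15 × 0.5 × 0.183/0.106 = −12.95. This gives (0.894 × 1.54 − 0.053 × 12.95)/0.947 = 0.73 lb, about half of 1.54.
- *Equal removal.* If 7 of 66 are removed in both arms with the same r, the expected difference is zero and the simulated type I error is about 0.026 to 0.035.

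**What the early termination visit covers.** It can supply a week-16 weight for the ITT and mITT analyses if the attempt succeeds. It does not recover the visits skipped between removal and week 16, and it does not return anyone who missed a visit to Completers. Read literally, 6.7 does not extend the attempt to a participant whom the investigator removes, whereas 10.5 refers to a participant's withdrawal in general.

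**The case against.** The strongest reply is that the rule is permissive, is restrained by the instruction that "unnecessary withdrawal of participants should be avoided", and is backed by a planned week-16 weigh-in. All three are true. They lower the likely size of the problem but leave an undefined discretionary ground in place, with retrieval that is only attempted.

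Compliance need not mean diet adherence. Inclusion criterion 5 uses the word for the visit schedule and exclusion criterion 20 uses it for the protocol as a whole. Someone removed for not attending is already missing, and keeping that person enrolled would recover little. This stands, and is itself a reason not to leave the term undefined.

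A reader might infer that the rule contradicts intention-to-treat or the adherence objective. It does not. Removed participants remain in the ITT population as defined, and the adherence correlations can still be run, over a narrower range.

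A reader might also infer that the MAR condition is broken. The documents do not show this. Earlier weights and adherence scores are recorded in all arms, and removal that depends on them can be compatible with MAR if the imputation model uses them. SAP 10.0 names no imputation variables, no fallback and no sensitivity analysis for data not missing at random, so the imputation is threatened rather than invalid.

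Finally, the case for unequal detection rests on TSFL. MEDD and Control share the same clinic visits and adherence scale, so it barely touches the MEDD comparison. Nor do the documents say that coaching information reaches the investigator who decides on removal.

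**Conclusion.** The concern holds as a risk. Investigator removal for compliance can create avoidable missing data that are related to outcome and may be unequal between arms, chiefly in TSFL against Control. The early termination visit mitigates this incompletely.

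The figures of about 0.9 to 2.1 lb, and type I error of about 0.033 to 0.08, rest on four conditions together: about 10% removed, in one arm only, no retrieval, and observed-case analysis. The documents give no removal rate, so this is a conditional range and not a forecast. It does not describe the planned ITT analysis with multiple imputation.

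The stronger reading, that the rule removes poor responders and makes the week-16 weights informatively missing, is not supported: the text permits removal rather than calling for it, names compliance rather than response, and plans a week-16 weigh-in. What remains justifies a change because the change is cheap.

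**What to change.** 1. In Protocol 10.5, delete compliance as a ground for removal from the study. Leave the medical grounds unchanged.
2. State there that participants who do not follow their plan stay in follow-up and are weighed at all remaining scheduled visits, as Protocol 6.8 and 10.5 already provide for the low-BMI group. This concerns follow-up only and sets no dietary rule.
3. Align 6.7 with 10.5 so that the week-16 weight is sought from every randomized participant, whoever initiated the withdrawal, and resolve the timing wording in 10.5.

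If removals on this ground have already occurred, report them by arm as their own category, and add a sensitivity analysis that does not assume MAR, such as delta-adjusted or control-based imputation.

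The cost is a short protocol amendment and visits already in the schedule. The downside is some staff effort on poorly engaged participants.
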